5.1.3. Tertiary Endpoints

Not applicable.

5.1.4. Other Efficacy Endpoints

5.1.4.1. Exploratory Endpoints

Analyses of exploratory endpoints will not be included in the CSR.

5.2. Safety

The primary endpoint of this study is the safety and tolerability of SBC-103 in subjects with MPS IIIB. The safety assessments will include the following:

- Incidence of treatment emergent adverse events (TEAEs), treatment emergent serious adverse events (TESAEs), and infusion-associated reactions (IARs) which are adverse events of special interest (AESI).
- Incidence of anti-drug antibodies (ADA) including ADA titer by time point, peak ADA titer, and ADA titer status (positive/negative), and the effect of ADAs on the safety of SBC-103, including the relationship between ADA-positive subjects and the incidence of IARs.

5.2.1. Adverse Events (AEs)

Adverse events are defined in Protocol Section 7.1. Also refer to Appendix 9.4.3 of this SAP for special handling of AE partial dates. Any AE that occurs after the first dose of SBC-103 in Part A is considered a treatment emergent adverse event (TEAE). AEs will be summarized cumulatively over the entire study and separately for Part C.

5.2.2. Vital Signs

Vital signs will be provided in a listing. The following vital signs were recorded at the times in Parts A, B and C as specified in Appendix 9.1: systolic and diastolic blood pressure (millimeters of mercury (mmHg)), heart rate (beats/minute), respiratory rate (breaths/minute), and temperature (degrees Celsius (°C) or degrees Fahrenheit (°F)).

5.2.3. Laboratory Assessments

Serum chemistry, hematology, urinalysis including coagulation, renal function, liver function, CSF, and assessment of ADAs related testing will be performed as per the SOA. Details on specific laboratory assessment timing in Parts A, B and C are provided in Appendix 9.1. All laboratory results will be provided in listings.

5.2.4. Other Safety Assessments of Special Interest

5.2.4.1. Anti-Drug Antibodies (ADA)

Patients will be monitored for the development of antibody production against SBC-103 at the times specified in the Part C SOA (Appendix 9.1.4). Serum will be collected and analyzed for the presence of ADA, and if positive, further analyzed for titer, and characterization of response (e.g., positive/negative).

5.2.4.2. ECG

Analyses of electrocardiogram (ECG) data will not be included in the CSR.

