3.4 Study Endpoints

3.4.1 Primary Endpoint

The primary endpoint of this study is safety and tolerability of SBC-103 in subjects with MPS IIIB. The safety assessments will include the following:

- Incidence of AEs, SAEs, and IARs;
- Changes from baseline in clinical laboratory tests (hematology, serum chemistry, and urinalysis) and CSF findings (cell counts, glucose, and protein);
- Changes from baseline in 12-lead electrocardiograms (ECGs);
- Changes in vital signs during and post-infusion, relative to pre-infusion values;
- Physical examination findings;
- Use of concomitant medications/therapies;
- Assessment of ADAs, including seroconversion rate, time to seroconversion, and ADA titer by time point, peak ADA titer, and ADA titer status (positive/negative), and the effect of ADAs on the safety of SBC-103, including the relationship between ADA-positive subjects and the incidence of IARs.

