8.4 Safety Analysis

Safety analyses may be performed for Parts A, B, C, and/or all 3 study parts (ie, the entire study). Descriptive summaries of data will be presented overall for all treated subjects and by dose group, as appropriate. Details of these analyses, including how baseline values are defined, will be specified in the statistical analysis plan (SAP).

Descriptive statistics will be computed for safety parameters, as appropriate. Number and percentage of subjects who discontinued from the study because of AEs, will be tabulated across dose cohorts; severity and frequency of AEs and SAEs will also be tabulated across dose cohorts. All other safety data will be provided in listings. Baseline, within study, end-of-study, and change from baseline in physical examination findings, ECG, clinical laboratory values, and vital signs will be summarized by dose cohort.

The proportion of subjects with measurable antibodies to SBC-103 will be displayed. In addition, IARs will be tabulated by cohort and overall. Medications to treat IARs, including any medications for pretreatment, will also be presented by cohort and over the entire study period. SBC-103 infusions in which the rate was slowed or discontinued due to IARs will be detailed in a separate data listing.

Further statistical evaluations will be applied for select endpoints, if warranted. All baseline data and safety data collected during the study will be listed for each subject.

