Study NGLU-CL02, *A Phase I/II Open Label Study in MPS IIIB Subjects to Investigate the Safety, Pharmacokinetics, and Pharmacodynamics/Efficacy of SBC-103 Administered Intravenously,* is an open label, 3-part Phase I/II study designed to evaluate the safety, tolerability, pharmacokinetics, and pharmacodynamics/efficacy of intravenous (IV) administration of SBC-103 in subjects with mucopolysaccharidosis III, type B (MPS IIIB, Sanfilippo B) with evaluable signs or symptoms of developmental delay.

Study NGLU-CL02 is conducted in 3 parts: Part A (Initial therapy at 0.3, 1, or 3 mg/kg), Part B (Extended Therapy at 1 and/or 3 mg/kg), and Part C (Extended Therapy at 5 and/or 10 mg/kg).

Part A is designed to assess the safety, tolerability, pharmacokinetics (PK), and pharmacodynamics (PD)/efficacy of 3 escalating doses of SBC-103 dosed once every other week (QOW) over 24 weeks.

Part B is designed to assess the safety, tolerability, PK, and PD/efficacy of chronic dosing for an extended period of time and to allow for intra-subject dose modification based on available data.

Following Part A and prior to entering Part B, subjects will have a 4-week period of time off therapy (instead of the usual 2 weeks between doses that occurs with QOW dosing) in order to assess the impact of treatment interruption on safety, tolerability, and select PD/efficacy markers, including the assessment of reversibility of any observed on-therapy changes in heparan sulfate (HS).

Part C (added with Amendment 6 and based on preliminary safety and PK/PD data from Parts A and B) is designed to assess the safety, tolerability, PK, and PD/efficacy of SBC-103 at 5 and 10 mg/kg QOW, as well as to assess the effects on chronic dosing. Subjects will be followed on Part C until the end of the treatment period at 156 weeks (a period of between 90 and 110 weeks). Intra-subject dose modification is permitted in Part C (based on data review and Sponsor agreement) with the intent to treat subjects with the lowest potentially efficacious dose that is safe and tolerable.

The protocol can be referenced for additional details. The Part C Schedule of Assessments (SOA) is attached in Appendix 9.1.4 of this Statistical Analysis Plan (SAP).

On 11 Jul 2017, Alexion decided to stop the clinical development program with SBC-103. A clinical study report (CSR) will detail the final demographic, disposition, exposure, and safety data of each study.

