4.1.1. Primary Objective

The primary objective of this CSR SAP is to evaluate the safety and tolerability of IV administration of SBC-103 in subjects with mucopolysaccharidosis III, type B (MPS IIIB, Sanfilippo B) with evaluable signs and symptoms.

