7.1.3.3. Medical / Surgical History and Baseline Physical Examination

Medical/surgical history and physical examination data will not be included in the CSR.

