7.3.3.3.2. ECG

Analyses of ECG data will not be included in the CSR.

8. **REFERENCES**

Statistical Analysis Plan {01 Sep 2017, Version 1.0}

9. **APPENDICES**

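### The SAP keeps safety as its primary objective but leaves ECG and physical-examination findings, two of seven primary-endpoint components, out of every output, and derives neither seroconversion rate nor time to seroconversion

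*SAP*

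**What the plan says.** Protocol 3.4.1 defines the primary endpoint, safety and tolerability, through seven components. One is "Changes from baseline in 12-lead electrocardiograms (ECGs"); another is physical-examination findings. The ADA component is spelled out as "including seroconversion rate, time to seroconversion, and ADA titer by time point", followed by peak titer, positive/negative status and the effect of ADA on safety. Protocol 8.4 plans summaries of ECG and examination findings by dose cohort and adds: "All baseline data and safety data collected during the study will be listed for each subject".

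SAP Section 4 records that development was stopped on 11 July 2017 and says the report "will detail the final demographic, disposition, exposure, and safety data of each study". SAP 4.1 declares a reduced subset of the protocol analyses, names safety among the data retained, and confines output to the items in SAP 4.1.4. Secondary and exploratory objectives are dropped. The primary one is not: "The primary objective of this CSR SAP is to evaluate the safety and tolerability of IV administration of SBC-103".

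Neither ECG nor physical examination is on the 4.1.4 list. Two sections exclude ECG outright (5.2.4.2: "Analyses of electrocardiogram (ECG) data will not be included in the CSR"; 7.3.3.3.2: "Analyses of ECG data will not be included in the CSR"), and 7.1.3.3 adds "Medical/surgical history and physical examination data will not be included in the CSR". For ADA, SAP 5.2, 7.3 and 7.3.3.3.1 plan confirmed status at each assessed visit, titer by time point, peak titer, neutralizing antibodies, and infusion-associated reactions (IARs) by ADA positivity. Seroconversion is not mentioned.

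**The concern.** Ending development explains why PK, PD and efficacy analyses were dropped. It does not by itself explain why parts of the one objective that was kept are missing, when laboratory, CSF, vital-sign and concomitant-medication data were kept as plain listings.

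The protocol has investigators classify each ECG abnormality as clinically significant or not (5.1.7) and record abnormal examination findings in the case report form (5.1.5). Under the SAP, such a finding reaches the report only if it was also recorded as an adverse event. This is a first-in-human study in children aged 2 to under 12. The rat no-effect level rested on vascular inflammation in heart and lungs (Protocol 1.3), and cardiac arrhythmia is named as a possible sign of an acute IAR (Protocol 7.1.3). The two monkey studies summarised in Protocol 1.3 attributed no microscopic change to SBC-103, so the cardiac question is one to document rather than an established signal.

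For ADA, a proportion positive at each visit does not say how many children ever converted, or when.

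**Working it through.** **Step 1. Match the seven components of Protocol 3.4.1 to the SAP outputs.**

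| Component | Output under the SAP |
|---|---|
| AEs, SAEs, IARs | Tables and listings |
| Laboratory tests and CSF findings | Listing only |
| ECG | None |
| Vital signs | Listing only |
| Physical examination | None |
| Concomitant medications | Listing only |
| ADA | Tables, in part |

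Tally: 2 tabulated + 3 listed only + 2 absent = 7; 2/7 = 28.6% absent.

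The two exclusions are worded differently. The ECG sections exclude analyses; the loss of the ECG listing follows from the closed list in SAP 4.1 and 4.1.4. SAP 7.1.3.3 excludes the examination data themselves. Its heading refers to the baseline examination, but no post-baseline findings are on the 4.1.4 list either. Only baseline height, weight and BMI survive, as demographics (SAP 7.1.3.1).

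**Step 2. Match the ADA measures.** Protocol 3.4.1 names six: seroconversion rate, time to seroconversion, titer by time point, peak titer, status, and effect on safety including IARs. The SAP carries the last four. 6 − 4 = 2 missing.

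Why a per-visit proportion is not a substitute (assumed data): if 3 of 11 children were each confirmed positive at one visit, and the three visits differed, no visit would show more than 1/11 = 9.1%, while 3/11 = 27.3% had ever turned positive.

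**Step 3. Count the scheduled assessments.** SAP Section 4 puts time in Part C at 90 to 110 weeks, ending at Week 156. Part C entry is therefore between Week 156 − 110 = 46 and Week 156 − 90 = 66. Counting through Part C Week 24 from the schedules of assessments:

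- ECG, Part A: Screening, Day 0, Weeks 12 and 24 = 4. Part B: Week 36, plus Week 52 if entry is later than that = 1 to 2. Part C: Day 0 and Weeks 2, 12 and 24 = 4. Total 4 + 1 + 4 = 9 to 4 + 2 + 4 = 10 per child, or 99 to 110 for 11 children.
- Physical examination, Part A: Screening, Days 0 and 1, Weeks 4, 8, 12, 16, 20 and 24 = 9. Part B: every 4 weeks from Week 28 until entry = 5 (entry at Week 46) to 10 (entry at Week 66). Part C: Day 0 and Weeks 4, 8, 12, 16, 20 and 24 = 7, leaving out Day 1, which applies only to the first subject at each dose. Total 9 + 5 + 7 = 21 to 9 + 10 + 7 = 26 per child.

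These are scheduled visits, and they assume that each child reached Part C Week 24. More are scheduled afterwards. Protocol 5.1.7 warns that ECGs may not always be obtainable, so the number actually recorded may be lower.

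**The case against.** The strongest reply is that the reduction is declared and reasoned. SAP Section 4 gives the cause, SAP 4.1 sits under a heading about changes from the protocol, and each exclusion is stated openly. That stands. A reader might infer that the SAP had to justify each dropped item separately; nothing in either document requires it, and asking for it would be a preference. Openness does not, however, supply the missing data for an objective the SAP says it still addresses.

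On ADA, the only output that Protocol 8.4 specifies is the proportion of subjects with measurable antibodies, and SAP 7.3.3.3.1 delivers that. A reader might infer that ADA incidence is left undefined. It is not: it is put into practice as confirmed status at each assessed visit, and the pre-dose Day 0 visit is a scheduled ADA sample. First-positive days can also be read by hand, because SAP 5.2.3 includes ADA testing among the laboratory results to be listed and SAP 7 adds a study day relative to first dose to dated listings. What remains is narrower: no output gives the cumulative conversion count or the time that the endpoint definition names.

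A reader might also see a contradiction between SAP 5.2.4.1, which points to the Part C schedule for ADA, and SAP 5.2.3, which points to Parts A, B and C. The second contains the first, and the Part A and B schedules in the SAP appendices carry ADA rows. It is a narrow cross-reference.

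Finally, a clinically important ECG or examination finding should also be recorded as an adverse event, and all adverse events are listed. That limits the loss to findings not so recorded.

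**Conclusion.** The point holds as a gap in completeness. Two of seven primary-endpoint components appear in no output, contrary to the listing commitment in Protocol 8.4, and two of the six ADA measures named in Protocol 3.4.1 are not derived.

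It would go too far to conclude that the SAP has abandoned its primary objective or concealed safety data. AEs, SAEs, IARs and ADA status and titer are tabulated, laboratory and vital-sign data are listed, and the reduction is disclosed.

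The count of two in seven comes straight from the documents. The visit counts rest on the schedules and on the Part C duration in SAP Section 4, not on data known to have been collected. The ADA example uses assumed data. How much information is actually lost depends on how many ECG or examination abnormalities were not recorded as adverse events, and on how far ADA positivity came and went; the documents show neither. The change is worth making because it is cheap and alters what the report can state.

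**What to change.** 1. Add to SAP 4.1.4 and 7.3.3 two by-subject listings: ECG findings, with the investigator's clinical-significance classification, and physical-examination findings. Each should show the dose at the time of the assessment; SAP 7.3.1 already lists the target dose by visit.
2. Add one ADA summary to SAP 7.3.3.3.1: the cumulative number (%) of subjects who go from a negative sample before the first Part A dose to confirmed positive, and the time from the first Part A dose to the first confirmed positive. The Part C baseline would not serve, because Protocol 4.3.4 requires at least four doses at 3 mg/kg before Part C entry.
3. As an editorial tidy-up only, extend the cross-reference in SAP 5.2.4.1 to the Part A and B schedules.

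The cost is modest programming for an abbreviated report on 11 children, with ECG listings that may be incomplete. Any rate will be imprecise: even 0 of 11 leaves a two-sided 95% upper limit of 1 − 0.025^(1/11) = 28.5%. Listings and counts are therefore enough, and no comparison between dose groups is asked for.

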6. DATA SETS ANALYZED (STUDY POPULATIONS)

The following analysis sets will be used for the presentation and analysis of the data for the CSR. For further information on the processing of patient data utilized in creating the following study population analysis dataset(s)/subset(s) and baselines, please see Appendix 9.4.1.

6.1. Full Analysis Set (FAS)

Not applicable.

6.2. Per Protocol (PP) Set

Not applicable.

6.3. Safety Set

The Safety Analysis Set, defined as all patients for whom informed consent has been obtained, who have a confirmed diagnosis of MPS IIIB, and who have received any amount of SBC-103, will be used to summarize all safety and tolerability data.

6.4. Other Sets

Not applicable.

7. STATISTICAL ANALYSIS

All output will be sorted and labeled according to the International Conference on Harmonization (ICH) recommendations, and formatted to the appropriate page size(s).

For the analyses covered by this SAP, data analysis and presentation for this study is primarily descriptive in nature; therefore, no inferential analyses are planned. Selected data will be presented in by-patient data listings and summarized in tables across patients if appropriate.

Descriptive summaries will be presented for treated subjects overall and by dose assignment, as appropriate. Continuous data will be summarized using descriptive statistics including number of patients, mean, standard deviation (SD), median, minimum, maximum, Lower quartile (25th percentile) Q1, and Upper quartile (75th percentile) Q3; categorical data will be summarized by counts and proportions. No formal statistical hypothesis testing will be performed.

For this analysis, information will be displayed by the Part C dose assignment as follows: SBC-103 5 mg/kg – QOW and SBC-103 10 mg/kg – QOW. All data listings that contain an evaluation date will contain a relative study day (Rel Day). Pre-treatment and on-treatment study days are numbered relative to the day of the first dose of study drug which is designated as Relative Day 1. The preceding day is Day -1, the day before that is Day -2, etc. The last day of study drug is designated with an "L" (e.g., Day 14L).

7.1. Study Patients

7.1.1. Disposition of Patients

Patient enrollment and disposition including number of patients screened, enrolled, dosed, and percentage of patients who discontinued from the study, along with reasons for discontinuations will be tabulated and described in listings.

7.1.2. Protocol Deviations

Analyses of protocol deviations will not be included in the CSR.

7.1.3. Demographics, Disease Characteristics and History

7.1.3.1. Demographics

Demographic and baseline characteristics will be summarized descriptively. Age at study entry (years), gender, race, ethnicity, baseline weight, baseline height and baseline Body Mass Index (BMI) will be summarized. Listings will also be provided.

7.1.3.2. Disease Characteristics

Disease characteristics will not be included in the CSR.

7.1.3.3. Medical / Surgical History and Baseline Physical Examination

Medical/surgical history and physical examination data will not be included in the CSR.

7.1.4. Prior and Concomitant Medications / Therapies

All medications and treatments received by the patient during the study or within the preceding 4 weeks will be collected. Any medication or treatment received after the first dose of SBC-103 will be considered concomitant. Medications will be mapped to a generic term using the current Alexion version of World Health Organization (WHO) Drug Dictionary (WHO-DD). Medications will be classified using the Anatomical Therapeutic Chemical (ATC) classification system. All prior and concomitant medications/therapies will be provided in listings.

7.2. Efficacy Analyses

7.2.1. Primary Analysis

As stated above, the primary objective of this study is to evaluate the safety and tolerability of IV administration of SBC-103, and as such, there is no primary efficacy endpoint or analysis.

7.2.1.1. Handling of Dropouts or Missing Data

Partial dates will be handled as detailed in Appendix 9.4.3 including details for calculating calendar or chronological age, as necessary. Missing data will be handled as detailed below for each measure.

7.2.1.2. Subgroup Analysis

Not applicable.

7.2.1.3. Multicenter Studies

Four centers are participating in this study and the number of subjects at each center by assignment is not large enough to produce meaningful summaries by center; therefore analyses by center will not be performed. Data from all sites will be pooled together.

7.2.1.4. Hypothesis Testing and Significance Level

Data analysis and/or presentation for this study are primarily descriptive in nature; therefore, no inferential analyses are planned and p-values will not be provided.

7.2.1.5. Sensitivity Analyses

Not applicable.

7.2.2. Secondary Analyses

Analyses of secondary endpoints will not be included in the CSR.

7.2.2.1. Neurocognitive and Developmental Assessments

Analyses of neurocognitive and developmental assessments will not be included in the CSR.

7.2.2.2. MRI Findings

Analyses of MRI findings will not be included in the CSR.

7.2.2.3. Blood Brain Barrier (BBB) Integrity Assessments

CSF/serum albumin index (CSF-AI) assessments of BBB integrity will be provided in listings.

7.2.2.4. Pharmacokinetic and Pharmacodynamic Analyses

7.2.2.4.1. Pharmacokinetic Analyses

Analyses of pharmacokinetic (PK) data will not be included in the CSR.

7.2.2.4.2. Pharmacodynamic Analyses

Analyses of pharmacodynamic (PD) data will not be included in the CSR.

7.2.3. Tertiary Analyses

Not applicable.

7.2.4. Other Efficacy Analyses

Not applicable.

7.2.5. Exploratory Analyses

No exploratory analyses will be included in the CSR.

7.3. Safety Analyses

As stated above in Section 5.2, the primary objective of this study is the safety and tolerability of SBC-103 in subjects with MPS IIIB. Descriptive statistics will be computed for specified safety parameters using the Safety Analysis Set, as appropriate, including treatment emergent adverse events (TEAEs), treatment emergent serious adverse events (TESAEs), and infusion-associated reactions (IARs) which are adverse events of special interest (AESI). The incidence of anti-drug antibodies (ADA) including ADA titer by time point, peak ADA titer, ADA titer status (positive/negative), neutralizing antibodies, and the relationship between ADA-positivity and the incidence of IARs will be presented.

7.3.1. Study Duration, Treatment Compliance, and Exposure

Dosing administration information will be listed by patient number, Part C dose assignment, and visit and will present details on confirmation of SBC-103 administration, reasons SBC-103 was not administered, total # of vials used, target dose (mg/kg), and dose concentration (mg/mL). Exposure to study drug (SBC-103) related information will be listed by patient number, Part C dose assignment and visit. The stop/start dates/times, total actual volume of drug infused (mL), infusion rate (mL/hr), type of infusion (dosing or saline flush), rate reduction percentage

compared to previous infusion rate, and information on any modification to the infusion including reason for modification will be presented in the listings.

